18.1.6 Exposure**18.1.6.1 Dose level for the sensitivity analysis of the primary endpoint**

The IMP dose level during the last 3 days of treatment in the Treatment Period will be specified based on the information from the *Initial Dose/Dose Adjustment*-page of the eCRF.

Therefore, the last six scheduled IMP intakes of the Treatment Period, i.e., the last IMP of Part 1 and the 5 preceding intakes, will be considered, analogous to the pain intensity assessments considered for the primary endpoint assessment.

For each of the six considered IMP intakes, the dose level (1 to 5) of the dose as given in the eCRF will be determined based on the tapentadol PR and morphine PR dosing tables provided in the trial protocol. The most frequent dose level will then be used as IMP dose level during the last 3 days of treatment in the Treatment Period. In case several different dose levels occur equally often among these 6 time points, the highest dose level of these will be used.

18.1.6.2 Average daily doses during the Tapentadol Period

For the Tapentadol Period, the average daily doses of IMP per kg body weight will be determined for each four-week interval and summarized descriptively per interval. The timeframe of the i -th interval of subject j is defined as

$(Date of TP_{i-1,j}, Date of TP_{i,j}]$

where $TP_{i,j}$, $i = 1, \dots, 13$, is the i -th visit of subject j during the Tapentadol Period (excluding visits M1 and M2 for subjects who were allocated to morphine in the Treatment period). $TP_{0,j}$ is equal to Visit VE of subject j . $TP_{13,j}$ is equal to Visit F12M of subject j .

For subjects terminating the Tapentadol Period between two scheduled visits, i.e.,

$Date of TP_{i-1,j} < Date of Visit ET_j$

the average daily doses of IMP per kg body weight in the time interval

$(Date of TP_{i-1,j}, Date of Visit ET_j]$

will be determined and included in the descriptive summary of the time interval

$(TP_{i-1}, TP_i]$

In case of a missing intermediate visit, it will be artificially introduced for this analysis by dividing the available surrounding visit interval to two equally sized subintervals. Hence, if the i -th visit for a subject j is missing ($Date of TP_{i,j}$), this visit will be estimated as the midpoint of the surrounding visit interval $(Date of TP_{i-1,j}, Date of TP_{i+1,j}]$ and the two newly introduced timeframes $(Date of TP_{i-1,j}, Date of TP_{i,j}]$ and $(Date of TP_{i,j}, Date of TP_{i+1,j}]$ will be used for further calculations. In case the length of the available visit interval is not a multiple of 2, it will be splitted such that the first time interval is 1 day longer than the second one.

18.1.7 Compliance

Compliance to the IMP dose regimen (%) is defined as the amount of IMP actually taken by a subject divided by the expected IMP amount the subject should have taken in the respective period and multiplied by 100.

Expected IMP amount:

For each subject the *Initial Dose/Dose Adjustment*-page of the eCRF collects for every entry/dose adjustment i

- The dose level in mg, denoted by d_i
- The start date (DD MMM YYYY) of dose level d_i , denoted by $t_i^{(S)}$
- The information whether dose level d_i starts with the morning- or evening-dose of the start date. This will be denoted by $S_i^{(S)}$ and coded $S_i^{(S)} = 1$ for “evening”, $S_i^{(S)} = 2$ for “morning”.
- The end date (DD MMM YYYY) of dose level d_i , denoted by $t_i^{(E)}$
- The information whether dose level d_i ended with the morning- or evening-dose of the start date. This will be denoted by $S_i^{(E)}$ and coded $S_i^{(E)} = 1$ for “morning”, $S_i^{(E)} = 2$ for “evening”.

- The period the above information belongs to, either being Treatment Period or Tapentadol Period. This implies that at the End of Treatment Visit VE, the investigator has to fill out the *Initial Dose/Dose Adjustment*-page of the eCRF, entering end date and information on $S_i^{(E)}$ even if the subjects continues on tapentadol with the same dose.

Let p_l be the index of the maximum start/end date where period equals treatment ($l = 1$) or tapentadol ($l = 2$) and $p_0 := 0$.

The expected amount of IMP is calculated for each subject by:

$$\sum_{i=p_{l-1}+1}^{p_l} \left[d_i * \left(2 * \left(t_i^{(E)} - t_i^{(S)} - 1 \right) + S_i^{(S)} + S_i^{(E)} \right) \right], \quad l = 1,2$$

Actual IMP amount:

IMP kits will be dispensed at every visit, but only to cover treatment until the next visit.

The drug-accountability page of the eCRF assessed for every kit j

- Date of dispense $t_j^{(D)}$
- IMP dose of kit j per tablet, denoted by d_j
- Number of tablets dispensed with kit j , denoted by $m_j^{(D)}$
- Date return $t_j^{(R)}$
- Number of tablets returned regarding kit j , denoted by $m_j^{(R)}$

First, for every kit j , the IMP amount in mg at dispense of kit j , denoted by $y_j^{(D)}$ and the remaining IMP amount in mg at return of kit j , denoted by $y_j^{(R)}$, will be calculated:

$$y_j^{(D)} = d_j * m_j^{(D)}$$

$$y_j^{(R)} = d_j * m_j^{(R)}$$

Kits that are returned before or at Visit VE, i.e., $t_j^{(R)}$ is lower or equal to the date of Visit VE, the difference $y_j^{(D)} - y_j^{(R)}$ is fully and uniquely assigned to Part 1.

Kits that are dispense after or at Visit VE, i.e., $t_j^{(D)}$ is greater or equal to the date of Visit VE, the difference $y_j^{(D)} - y_j^{(R)}$ is fully and uniquely assigned to Part 2.

Kits that are dispensed before Visit VE, i.e., $t_j^{(D)}$ is lower than the date of Visit VE, but returned after Visit VE due to any reason, i.e., $t_j^{(R)}$ is greater than the date of Visit VE, the difference $y_j^{(D)} - y_j^{(R)}$ cannot uniquely be assigned to either part. In this case, at Visit VE the investigator should remind the subject not to continue IMP intake from that kit, but the ones dispense at Visit VE as compliant with the protocol. As the IMP of that particular kit should have been taken during Part 1, this kit will also be assigned to Part 1 for statistical analysis.

Let \tilde{t} be the date of Visit VE.

Part 1

The actual amount of IMP will be calculated as:

$$\sum_{\{j: t_j^{(D)} < \bar{t}\}} (y_j^{(D)} - y_j^{(R)})$$

Part 2

The actual amount of IMP will be calculated as:

$$\sum_{\{j: t_j^{(D)} \geq \bar{t}\}} (y_j^{(D)} - y_j^{(R)})$$

18.1.8 Primary endpoint**18.1.8.1 Missing baseline pain intensity for the Treatment Period**

For descriptive statistics of the baseline pain intensity for the Treatment Period, missing baseline pain values will be considered as such.

For the derivation of the primary endpoint, the “responder” status of a subject, a missing baseline pain intensity value will be considered as missing, so that the responder criterion based on the baseline pain intensity cannot be assessed and therefore cannot lead to a “responder” status.

For the primary endpoint analysis (main analysis and sensitivity analyses if applicable), including baseline pain intensity as an explanatory variable in the analysis model, missing values will be imputed by the values resulting from the multiple imputation for the missing pain values during the 3 last days of treatment in the Treatment Period as explained in the “Handling missing data” paragraph of the following section. For those analyses based on primary endpoint data from multiple imputation, the corresponding imputed baseline values of the respective dataset will be used. For those analyses of the primary endpoint based on observed data, the average of the baseline values for the 200 multiple imputation datasets for a subject will be used for imputation of this missing baseline value.

18.1.8.2 Primary analysis**Calculating the confidence interval and p-value based on the Farrington-Manning test**

Maximum-Likelihood estimates \hat{p}_T , \hat{p}_C for p_T , p_C will be obtained fitting a logistic regression model to the response using baseline pain intensity, age group, treatment and underlying pain condition as explanatory variables.

Baseline pain intensity is measured on different scales (FPS-R, VAS) depending on the age group of the subject. To synchronize the scales, for the logistic regression the FPS-R baseline pain intensity, within a range of [0,10], will be multiplied by 10. This transformation allows for a common range of baseline pain intensities of [0,100].

The method introduced by Farrington and Manning (1990) will be used to determine the variance estimator

$$\hat{v}_0 = \frac{\tilde{p}_T(1 - \tilde{p}_T)}{N_1} + \frac{\tilde{p}_C(1 - \tilde{p}_C)}{N_2}$$

with

- N_1 : sample size of tapentadol arm in Part 1
- N_2 : sample size of morphine arm in Part 1
- $\tilde{p}_C = \hat{p}_T + \delta$
- $\tilde{p}_T = 2 * u * \cos(w) - b/(3a)$
 - $r = N_2/N_1$
 - $a = 1 + r$
 - $b = -[1 + r + \hat{p}_T + r * \hat{p}_C - \delta * (r + 2)]$
 - $c = \delta^2 - \delta(2 * \hat{p}_T + r + 1) + \hat{p}_T + r * \hat{p}_C$
 - $d = \hat{p}_T * \delta * (1 - \delta)$
 - $w = (\pi + \cos^{-1}(v/(u^3)))/3$
 - $v = b^3 / (3a)^3 - (b * c) / (6a^2) + d / (2a)$
 - $u = \text{sign}(v)[b^2 / (3a)^2 - c / (3a)]^{1/2}$

Based on \hat{p}_T, \hat{p}_C and the Farrington-Manning variance estimate \hat{v}_0 , the realization T_0 of the test-statistic

$$T = \frac{\hat{p}_T - \hat{p}_C + \delta}{\sqrt{\hat{v}_0}}$$

will be obtained. The p-value of the Farrington-Manning test regarding non-inferiority will be determined by calculating the probability

$$p = P(X > T_0)$$

where X is a standard normally distributed random variable.

Furthermore the 80% -confidence interval of the difference in responder rates

$$CI = [\hat{p}_T - \hat{p}_C - z_{1-\alpha} * \sqrt{\hat{v}_0}, \hat{p}_T - \hat{p}_C + z_{1-\alpha} * \sqrt{\hat{v}_0}]$$

will be determined, where $z_{1-\alpha}$ is the $(1 - \alpha)$ -quantile of the standard normal distribution with $\alpha = 0.1$.

Handling missing data

The above elaboration describes the analysis procedure in the event of no missing data. For the proposed imputation method missing at random (MAR) will be assumed.

Information on the pain assessments during the last 3 days of treatment in the Treatment Period might only be partially available. In this case *Multiple Imputation* will be used to impute missing values:

1. For each treatment group, a multivariate normal distribution for the vector of the age group (AGE), underlying pain condition (PAIN) and baseline pain intensity (BASE), as well as the last 6 scheduled pain measurements during treatment of the Treatment Period, denoted by (Y_1, \dots, Y_6) , is assumed $(AGE, PAIN, BASE, Y_1, \dots, Y_6) \sim MVN(\mu, \Sigma)$. Missing observations are assumed to depend on the observed values of the subjects in the same treatment group. Therefore, in both treatment arms, missing pain assessments will be imputed using information from an imputation model that is only based on the subjects in the respective arm..

The multiple imputation will be performed once for all subjects using VAS, and once for all subjects using FPS-R. To ensure that the imputed values are within the range of the respective pain scale (0-10 for FPS-R and 0-100 for VAS), minimum and maximum values for the variable to be imputed should be specified.

The multiple imputations will be done via SAS PROC MI. The imputation model will be based on the default Markov chain Monte Carlo (MCMC) method for general patterns of missingness (Dmitrienko et al. 2005). A BY statement will be used to implement the imputation by treatment group. The variables will be given the following order: age group, pain condition, baseline pain, last 6 scheduled pain assessments starting with the earliest one.

For the sake of reproducibility of the results, the seed for pseudo-random number generation will be set to 550366.

The number K of imputed data sets will be set to 200, resulting in 200 complete data sets:

- Number of imputed data sets: $K = 200$

Imputed values for missing baseline pain intensities, to be used as explanatory variable in the logistic regression model, will also be obtained from the multiple imputation.

2. Each complete data set $k = 1, \dots, K$ will be analyzed as described above in case of no missing data up to the step where $\hat{p}_{T,k}$, $\hat{p}_{C,k}$ and the Farrington-Manning variance estimate $\hat{v}_{0,k}$ are obtained. Let $\hat{\theta}_k = \hat{p}_{T,k} - \hat{p}_{C,k}$.

3. With $(\hat{\theta}_1, \sqrt{\hat{v}_{0,1}}), \dots, (\hat{\theta}_{200}, \sqrt{\hat{v}_{0,200}})$ as input, PROC MIANALYZE will be applied to obtain the test statistic T_{MI} and confidence interval CI_{MI} as follows:

- Multiple imputation estimate: $\hat{\theta}_{MI} = \frac{1}{K} \sum_{k=1}^K \hat{\theta}_k$
- Within-imputation component of variance: $\hat{\sigma}_w^2 = \frac{1}{K} \sum_{k=1}^K \hat{\sigma}_k^2$
- Between-imputation component of variance: $\hat{\sigma}_b^2 = \frac{1}{K-1} \sum_{k=1}^K (\hat{\theta}_k - \hat{\theta}_{MI})^2$
- Multiple imputation variance estimate: $\hat{\sigma}_{MI}^2 = \left(1 + \frac{1}{K}\right) \hat{\sigma}_b^2 + \hat{\sigma}_w^2$
- Test statistic: $T_{MI} = \frac{\hat{\theta}_{MI} + \delta}{\hat{\sigma}_{MI}}$
- Degrees of freedom: $\vartheta = (K - 1) \left[1 + \frac{\hat{\sigma}_w^2}{(1 + \frac{1}{K}) \hat{\sigma}_b^2} \right]^2$
- Confidence interval:

$$CI_{MI} = [\hat{\theta}_{MI} - \hat{\sigma}_{MI}^2 t_{\vartheta, 1-\alpha}, \hat{\theta}_{MI} + \hat{\sigma}_{MI}^2 t_{\vartheta, 1-\alpha}]$$

with $t_{\vartheta,1-\alpha}$ being the $(1 - \alpha)$ -quantile of the t -distribution with $\alpha = 0.1$ and ϑ degrees of freedom.

Non-inferiority of tapentadol versus morphine will be assigned if the lower bound of CI_{MI} exceeds the negative non-inferiority margin $-\delta = -0.2$. Additionally, the realization $T_{MI,0}$ of the test statistics T_{MI} will be used to compute the one-sided p-value

$$p = P(X > T_{MI,0})$$

where X is a t-distributed random variable with ϑ degrees of freedom.

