5.2 Sample size

The sample size was estimated to reject the null hypothesis of the inferiority of tapentadol PR to morphine PR when comparing responders evaluated at the end of the 14-day Treatment Period (Part 1, i.e., the primary endpoint). The percentage of responders in both treatment arms is estimated to be 80% based on data from previous trials and extrapolation to the trial population under investigation. The non-inferiority margin is set to a difference of 20% for the primary endpoint (i.e., responder rate, see Section 13.1).

To show the non-inferiority of tapentadol PR compared to morphine PR using a Farrington Manning (1990) test by a non-inferiority margin of 20% with at least 80% power and a 1-sided significance level of alpha = 0.1, 69 subjects are required in the FAS, assuming a 2:1 randomization of tapentadol PR:morphine PR.

A one-sided alpha of 0.1 is considered appropriate based on a method proposed by Hlavin et al. (2016). The approach makes use of prior knowledge and the concept of extrapolation from a larger population to a small target population (i.e., pediatric population), to reduce the burden of evidence in pediatrics by relaxing the Type I error, while controlling a certain posterior belief, i.e., confidence after successful pediatric trials, in effectiveness of the drug in children.

Further details for the application of the concept of Hlavin et al. (2016) in the context of this trial are provided in a separate document that is available upon request.

The periodic reviews of the Data Monitoring Committee (DMC) (see Section 6.3) during the trial address only safety and no efficacy data and thus have no impact on the sample size.

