13.1.1 Main analysis

The FAS will be the primary analysis set.

Let p_T, p_C be defined as

p_T : expected value of the responder rate in the tapentadol arm

p_C : expected value of the responder rate in the morphine arm

Let the non-inferiority margin be $\delta = 0.2$.

The primary null hypothesis to be tested in this trial is that treatment with tapentadol is inferior to treatment with morphine, i.e.,

$$H_0: p_T - p_C \leq -\delta$$

The alternative hypothesis is that treatment with tapentadol is non-inferior to treatment with morphine, i.e.,

$$H_1: p_T - p_C > -\delta$$

Maximum-Likelihood estimates \hat{p}_T, \hat{p}_C for p_T, p_C will be obtained fitting a logistic regression model to the response using baseline pain intensity, age group, treatment and underlying pain condition as explanatory variables.

The method introduced by Farrington and Manning (1990) will be used to determine the variance estimator \hat{v}_0 .

Based on \hat{p}_T, \hat{p}_C and the Farrington-Manning variance estimate \hat{v}_0 , the p-value of the Farrington-Manning test regarding non-inferiority and the 80% -confidence interval (CI) of the difference in responder rates will be determined.

Non-inferiority of tapentadol versus morphine will be assigned if the lower bound of the CI exceeds the negative non-inferiority margin $-\delta = -0.2$.

For details on the methods and formulas used, see Section [18.1.8](#).

Handling missing data

The primary efficacy endpoint consists of two parts. Information on the first part, *Completion of the 14-day Treatment Period*, will always be available. However information on the pain assessments during the last 3 days of treatment in the Treatment Period might only be partially available. In this case Multiple Imputation will be used to impute missing values. A detailed description of this method can be found in Section [18.1.8](#).

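### The SAP sets the null morphine rate in the Farrington-Manning variance to the estimated, not the restricted, tapentadol rate plus 0.2, so the primary interval is too narrow or undefined around the planned 80%

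*SAP*

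**What the plan says.** SAP 13.1.1 tests the null hypothesis p_T - p_C ≤ -δ with δ = 0.2 and says that, from the two estimated rates and the Farrington-Manning variance, "the p-value of the Farrington-Manning test regarding non-inferiority and the 80% -confidence interval (CI) of the difference in responder rates will be determined". The claim of non-inferiority is made if the lower limit lies above -0.2.

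SAP 18.1.8.2 gives the formulas. The estimated rates (p̂_T and p̂_C in what follows) "will be obtained fitting a logistic regression model to the response using baseline pain intensity, age group, treatment and underlying pain condition as explanatory variables". Then: "The method introduced by Farrington and Manning (1990) will be used to determine the variance estimator", namely

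v̂₀ = p̃_T(1 - p̃_T)/N₁ + p̃_C(1 - p̃_C)/N₂.

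The restricted tapentadol rate p̃_T is the closed-form root of a cubic with coefficients a, b, c and d. The restricted morphine rate is printed as p̃_C = p̂_T + δ, with a hat on the right-hand side.

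On planning, SAP 5.2 says: "The percentage of responders in both treatment arms is estimated to be 80% based on data from previous trials". It also states that "with at least 80% power and a 1-sided significance level of alpha = 0.1, 69 subjects are required in the FAS". The allocation is 2:1 in favour of tapentadol.

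**The concern.** The Farrington-Manning variance is evaluated at the maximum-likelihood rates under the null boundary, p_T - p_C = -δ. Both restricted rates must lie on that boundary, so p̃_C = p̃_T + δ. The printed line mixes a restricted tapentadol rate with an unrestricted one, and the resulting pair meets the constraint only when p̂_T happens to equal p̃_T.

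The consequence is visible without any computation. With δ = 0.2 the printed p̃_C reaches 1 at p̂_T = 0.80 and exceeds 1 above it. The morphine contribution to the variance is then zero or negative, exactly where the trial expects its result.

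This variance enters the test statistic, the p-value, the deciding 80% interval and, through its square root, the analysis of each of the 200 imputed data sets. The one-sided level has already been relaxed to 0.1, so there is little room for further unplanned inflation.

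**Working it through.** **Inputs.** δ = 0.2 (SAP 13.1.1). Planned rates 80%/80%, one-sided α = 0.1, N = 69 and 2:1 allocation (SAP 5.2), so N₁ = 46 tapentadol and N₂ = 23 morphine. z at 0.90 = 1.2816. Raw proportions stand in for the logistic-model estimates, and no data are missing.

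**The plan's own figure.** With p̃_C = p̃_T + δ, exact binomial enumeration at 80%/80% gives power of 78.5% at N = 66 and 80.8% at N = 69. So 69 is consistent with the correct formula. (The asymptotic formula gives 78.4% at 69.)

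**Is the rest of the block right?** At p̂_T = p̂_C = 0.80, r = 23/46 = 0.5 and:

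- a = 1 + 0.5 = 1.5
- b = -(1 + 0.5 + 0.8 + 0.4 - 0.2 × 2.5) = -2.2
- c = 0.04 - 0.2 × (1.6 + 0.5 + 1) + 0.8 + 0.4 = 0.62
- d = 0.8 × 0.2 × 0.8 = 0.128

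The SAP's closed form gives p̃_T = 0.6942. Direct maximisation of the likelihood under p_C = p_T + 0.2 gives the same value. The cubic therefore already assumes p̃_C = p̃_T + δ; only the p̃_C line departs from it.

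**Variance at 80%/80%.** The tapentadol term is 0.6942 × 0.3058/46 = 0.00461 in both versions.

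- Correct: p̃_C = 0.8942, morphine term 0.8942 × 0.1058/23 = 0.00411, v̂₀ = 0.00873, SE 0.0934, lower limit 0 - 1.2816 × 0.0934 = -0.120.
- As printed: p̃_C = 1.00, morphine term 0, v̂₀ = 0.00461, SE 0.0679, lower limit -0.087.

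The ratio of standard errors is 0.0679/0.0934 = 0.73, so the interval is 27% too narrow.

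**Other estimated rates (tapentadol/morphine).**

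| Rates | Printed p̃_C | Printed morphine term | Printed SE | Correct SE |
|---|---|---|---|---|
| 75%/80% | 0.95 | 0.0021 | 0.0827 | 0.0976 |
| 80%/80% | 1.00 | 0 | 0.0679 | 0.0934 |
| 85%/85% | 1.05 | -0.0023 | 0.0448 | 0.0844 |
| 90%/90% | 1.10 | -0.0048 | none (v̂₀ = -0.0008) | 0.0752 |

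The whole variance turns negative from p̂_T of about 0.89.

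**Operating characteristics**, enumerating all 47 × 24 outcomes:

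- At true 80%/80%, the observed tapentadol rate exceeds 80% in 56% of trials, and v̂₀ is zero or negative in 5.7%.
- At true 80%/80%, the nominal 80% interval covers the true difference in 53.5% of trials as printed, with the 5.7% having no interval. With the correct line, coverage is 74.9%.

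Exact one-sided error at the margin:

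| True rates | Correct | Printed, undefined counted as failure | Printed, negative variance set to zero |
|---|---|---|---|
| 60%/80% | 10.5% | 12.0% | 12.0% |
| 70%/90% | 11.2% | 14.3% | 14.5% |
| 75%/95% | 11.2% | 16.9% | 18.4% |

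**A verdict that flips.** For 37/46 (80.4%) against 21/23 (91.3%) the difference is -0.109. The correct lower limit is -0.211, which fails. The printed formula gives -0.189, which passes.

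**The case against.** The strongest objection concerns the text. The point rests on one accent in a formula read from PDF by a program, and there are signs of lost marks nearby. SAP 18.1.7 shows one date symbol with two different accents. The Amendment 01 change log (SAP 17.2) lists the lines for b, c and d as changed, although the two versions read identically in the available text. If the signed SAP prints p̃_T + δ, nothing remains of this point. Against that, the other hats and tildes on p_T and p_C in the block sit where the method needs them, and no other section restates the line. The check is necessary, but it is not a reason to leave the line alone.

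Second, the protocol and SAP name the right method, the sample size agrees with it, and a programmer who obtains a probability above 1 might notice. That is fair: the harm arises only if the line is coded as printed. But SAP 18.1 exists to specify the programming. If the program silently departs from it, the SAP no longer describes the primary analysis.

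Third, the effect on decisions is smaller than the effect on the standard error. The correct test already runs at 10.5% to 11.2%. At 60%/80%, the null point that matches the planned morphine rate, the printed line adds 1.5 percentage points. The larger excesses need morphine rates of 90% to 95%. At true 80%/80%, the verdict differs in 3.8% of trials if a negative variance is set to zero, or in 9.5% (3.8% + 5.7%) if those trials count as failures. The SAP specifies neither convention. This limits the size of the problem but does not remove it.

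**Conclusion.** As printed, the line is wrong: it contradicts both the method that the SAP names and the SAP's own cubic. Near the planned rates the primary interval is too narrow, by 27% at 80%/80%. From a tapentadol estimate of about 0.89 it does not exist. The one-sided error at the margin rises from 10.5% to 12.0% at 60%/80%, and from 11.2% to between 16.9% and 18.4% at 75%/95%.

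The figures assume 46 and 23 subjects, raw rather than covariate-adjusted rates, and complete data. With missing data the deciding interval is the multiple-imputation one, so the worked flip applies to the complete-data case only. The two versions coincide when the observed difference is exactly -0.20. The sample size of 69 is not affected. The conclusion is conditional on the signed SAP carrying the hat that appears in the available text; if it does, the line must be corrected before the primary analysis is run.

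**What to change.** In SAP 18.1.8.2, define the restricted morphine rate as p̃_C = p̃_T + δ. First check the line in the signed PDF. Then confirm that the analysis program uses the corrected line, for example by checking that 80%/80% with 46 and 23 subjects returns restricted rates of 0.694 and 0.894 and a standard error of 0.0934. The cost is a one-symbol correction and a short program check. Neither the design nor the sample size changes.

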13.1.3 Other analysis

Summary statistics for the primary endpoint will be provided for each level of the subgroups defined in Table 4 and for subgroups of subjects with and without a neuropathic pain component (based on information from the Pain Condition page of the eCRF at Visit V1).

Furthermore, as exploratory analyses, for subgroup levels that include at least 5 subjects in each of the two treatment groups, the differences in Maximum Likelihood-estimators between morphine and tapentadol and their 80% confidence intervals obtained by the Farrington Manning method will be provided and illustrated together in one forest plot.

In addition, summary statistics for the primary endpoint per IMP dose level during the last 3 days of treatment in the Treatment Period will be presented.

Based on observed, non-imputed data, the individual criteria considered for the response assessment for the FAS will be summarized descriptively. The following categories will be presented:

- Completion of the 14-day Treatment Period (yes/no).
- Average pain during the last 3 days of treatment in the Treatment Period <50 (VAS) or <5 (FPS-R) (yes/no).
- Average pain reduction for the last 3 days of treatment during the Treatment Period from baseline of ≥20 (VAS) or ≥2 (FPS-R) (yes/no).
- Completion of the 14-day Treatment Period and average pain during the last 3 days of treatment in the Treatment Period <50 (VAS) or <5 (FPS-R).
- Completion of the 14-day Treatment Period and average pain reduction for the last 3 days of treatment during the Treatment Period from baseline of ≥20 (VAS) or ≥2 (FPS-R).
- Completion of the 14-day Treatment Period, but average pain during the last 3 days of treatment in the Treatment Period ≥50 mm (VAS) or ≥5 (FPS-R) and average pain reduction for the last 3 days of treatment during the Treatment Period from baseline <20 mm (VAS) or <2 (FPS-R).

The pain related criteria will be presented using VAS for all subjects, using FPS-R for all subjects and using VAS for subjects 12- <18 years or FPS-R for subjects 6- <12 years.

The analysis of the primary endpoint will also be repeated using the following modifications in the definition of a responder:

- Using VAS for all subjects 6- <18 years old to assess the pain related response criteria (average pain <50 or average reduction from baseline pain ≥20 on a VAS).

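### The reported 80% confidence interval uses the variance restricted at the -20-point margin in both limits, so it covers about 74-76% rather than 80% when the two responder rates are similar (about 70-85%); the complete-data non-inferiority decision is not affected

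*SAP*

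**What the plan says.** SAP section 5.2 sets the design. The expected rates are equal: "The percentage of responders in both treatment arms is estimated to be 80" per cent. "The non-inferiority margin is set to a difference of 20% for the primary endpoint". The size follows: "with at least 80% power and a 1-sided significance level of alpha = 0.1, 69 subjects are required in the FAS". Allocation is two to one in favour of tapentadol, which gives 46 and 23 subjects.

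For the analysis, section 18.1.8.2 states: "The method introduced by Farrington and Manning (1990) will be used to determine the variance estimator". The restricted rates behind it differ by exactly delta = 0.2. The resulting v0 is the denominator of the test statistic. The same section then gives "Furthermore the 80% -confidence interval of the difference in responder rates" as the estimated difference plus or minus z(0.90) times the square root of that same v0. Nothing is re-solved for the limit being computed.

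The decision rule in section 13.1.1 is "Non-inferiority of tapentadol versus morphine will be assigned if the lower bound of the CI exceeds the negative non-inferiority margin", that is, -0.2. With missing data, section 18.1.8.2 feeds the square root of v0 from each of 200 imputed data sets into the pooling step. For subgroup levels with at least 5 subjects per arm, section 13.1.3 plans the differences and "their 80% confidence intervals obtained by the Farrington Manning method will be provided and illustrated together in one forest plot". Neither document discusses coverage away from the margin.

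**The concern.** A variance computed under a difference of -20 points is the right denominator for a test at -20 points. It is not the sampling variance when the true difference is somewhere else. If the arms respond about equally, as the sample size assumes, the variance could be too small and the interval too narrow for its 80% label.

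The interval is the trial's main statement of how much worse or better tapentadol might be, and it will be read beyond the yes/no at -0.2. One-sided alpha is already relaxed to 0.1, so the confidence level that is printed should at least be the one delivered. The same method also feeds the subgroup forest plot.

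**Working it through.** **Inputs.** From SAP 5.2: N = 69 at 2:1 (46/23), 80% in both arms, margin 0.20, one-sided alpha 0.1. From SAP 18.1.8.2: v0 = p̃_T(1 - p̃_T)/N1 + p̃_C(1 - p̃_C)/N2, and limits = difference ± 1.2816 × √v0. The SAP prints the restricted morphine rate as the unrestricted tapentadol estimate plus delta. I read it as the restricted tapentadol rate plus delta.

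**Reproducing the plan's own figure.** At observed rates of 0.80/0.80 the restricted rates are 0.6942 and 0.8942.

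- v0 = 0.6942 × 0.3058/46 + 0.8942 × 0.1058/23 = 0.00461 + 0.00411 = 0.00873 (before rounding the terms).
- N = (1.2816 + 0.8416)² × (69 × v0)/0.20² = 67.9, which becomes 69 at 2:1.
- Exact binomial power of the test at 46/23 is 80.8%. The stated 69 is reproduced.

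**Variance at equal rates.** The true variance at 80%/80% is 0.16/46 + 0.16/23 = 0.00348 + 0.00696 = 0.01043. The restriction pushes the smaller arm up to 89%, where binomial variance is low, and this outweighs the increase in the larger arm. The planned standard error is 0.914 of the correct one.

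**Effect on the limits at observed 0.80/0.80.**

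- Planned: ±1.2816 × √0.00873, so -12.0 to +12.0 points.
- Score inversion (restricted rates re-solved at each limit): -12.3 to +14.2 points.

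For attainable data, 37/46 against 18/23, the planned interval is -10.0 to +14.3 points and the score interval -10.3 to +16.5. The lower limit moves 0.3 points and the upper 2.2.

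**Exact coverage at 46/23** (full enumeration of both binomials, raw proportions, no missing data):

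| True rates, tapentadol/morphine | Planned interval | Score inversion |
|---|---|---|
| 80%/80% | 74.9% | 79.5% |
| 70%/70% | 75.3% | 80.1% |
| 75%/75% | 74.9% | not listed |
| 85%/80% | 74.2% | 79.8% |
| 85%/85% | 76.2% | not listed |
| 60%/80% (the margin) | 79.4% | not listed |
| 50%/50% | 79.3% | not listed |
| 90%/90% | 79.7% | 77.8% |

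At 80%/80% the planned interval lies wholly above the truth 11.6% of the time and wholly below it 13.5% of the time.

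**Decision.** Lower limit > -0.2 rearranges to (difference + 0.2)/√v0 > 1.2816, which is the planned test. Its exact rejection rate at 60%/80% is 10.5%.

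**Covariate adjustment.** The SAP uses rates from a logistic regression, so adjusted rates were simulated with 69 subjects and 80% response in each arm. Covariate effects were assumed, from none to strong. Coverage of the planned interval was 74-78%.

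**Subgroups** (sizes assumed; the documents give only the minimum of 5 per arm, and the protocol's 25% floor for ages 6 to <12 allows about 18 of 69, roughly 12/6). At 80%/80%:

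| Arm sizes | Planned interval | Score inversion |
|---|---|---|
| 10/5 | 67.5% | 73.0% |
| 12/6 | 67.3% | 72.0% |
| 14/7 | 68.0% | 72.2% |
| 5/5 | 77.8% | 77.8% |

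**The case against.** The strongest reply is that nothing the trial decides depends on this. The only formal use of the interval is the comparison of its lower limit with -0.2, and for complete data that comparison is the Farrington-Manning test itself. The section heading presents the interval as based on that test, so it can be read as chosen to agree with the p-value. The upper limit enters no rule, and the point estimate is untouched. This stands. A reader might infer that non-inferiority could be declared too easily. The complete-data formula does not support that.

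A second reply is that the shortfall is conditional. This also stands: coverage is near nominal at the margin, at 50%/50% and at 90%/90%, and at 90%/90% score inversion covers slightly less than the planned interval. Calling the upper limit invalid would be too strong. Its miss rate at 46/23 is 10.5-13.7% against 10% over the rates checked.

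Third, a reader might blame the restricted variance for all of the subgroup under-coverage. The figures do not support that. At 12/6, score inversion recovers 4.7 of the 12.7 points missing, and at 5/5 none of the 2.2. The rest is small-sample discreteness. The SAP also calls these analyses exploratory.

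Fourth, the exact figures are not for the full primary procedure with adjustment and imputation. That is fair; the adjusted simulation shows a similar but somewhat smaller shortfall.

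What the replies do not remove is that the interval carries an 80% label and falls short of it at the plan's own assumed rates.

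**Conclusion.** The point holds as a reporting defect worth correcting. At 46/23 the interval labelled 80% has exact coverage of about 74-76% for similar responder rates of roughly 70-85%, and 74.9% at the planned 80%/80%. Coverage is close to 80% at the margin and at 90%/90%. The error falls mainly on the upper limit, about 2 points in the worked examples. In small 2:1 subgroups at 80%/80% coverage can be as low as about 67%, but a proper score interval reaches only about 72-73% there.

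This rests on raw proportions, no missing data, the reading of the restricted morphine rate given above, and assumed subgroup sizes.

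The statement that the decision is unaffected covers the complete-data interval only. The multiple-imputation interval is printed with the pooled variance, not its square root, times the t quantile. As printed, its comparison with -0.2 therefore does not match the pooled test statistic in the same section. That needs clarifying, but it is not a consequence of the restricted variance.

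**What to change.** Keep the Farrington-Manning test and p-value at -0.2. Compute each reported limit by inverting the score statistic: for each candidate difference D, re-solve the restricted rates and v0 with delta replaced by -D, and find the D at which |difference - D|/√v0(D) = z(0.90). Use this for the main interval and the forest plot. At D = -0.2 it returns the planned statistic, so alpha, power and N = 69 do not change.

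For multiple imputation, at each candidate D recompute the restricted variance in every imputed data set and pool by Rubin's rules. Solve for the limit using the pooled standard error (not the pooled variance) times t, so that the comparison with -0.2 agrees with the pooled test statistic.

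Alternatively, label the present interval as test-based, for comparison with -0.2 only, and report a separate 80% score interval for estimation.

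The cost is a revised SAP formula, a root search in the program (with pooling repeated at each candidate value under imputation) and slightly wider reported intervals. Subgroup intervals remain approximate and should be described so.
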